## 9.9.5. Study Population Figures

Study F	Study Population Figures					
No.	No. Population IDSL / Example Shell Title Programming Notes Deliverable [Priority]					
Time to	Time to Withdrawal					
2.1.	SAF	POP_F01	Kaplan-Meier Plot of Time to Premature Discontinuation from Investigational Product		SAC [1]	

# 9.9.6. Safety Tables

Safety:	Tables				
No.	Population	IDSL / Example Shell	Title	Programming Notes	Deliverable [Priority]
Exposu	re				
2.1.	SAF	EX1	Summary of Exposure to Study Treatment	ICH E3	SAC [1]
BMD at	Total Hip				
2.2.	SAF	SAFE_T01	Summary of On-treatment Bone Mineral Density (g/cm^2) at the Total Hip		SAC [1]
2.3.	SAF	SAFE_T01	Summary of On-treatment Bone Mineral Density (g/cm^2) at the Total Hip by Gender		SAC [1]
2.4.	SAF	SAFE_T02	Summary of On-treatment Percentage Change in Bone Mineral Density (g/cm^2) at the Total Hip	Page by Gender	SAC [1]
2.5.	SAF	SAFE_T02	Summary of On-treatment Percentage Change in Bone Mineral Density (g/cm^2) at the Total Hip by Gender		SAC [1]
2.6.	SAF	SAFE_T03	Summary of On-treatment T and Z Scores for Bone Mineral Density at the Total Hip	Page by Gender	SAC [1]
2.7.	SAF	SAFE_T03	Summary of On-treatment T and Z Scores for Bone Mineral Density at the Total Hip by Gender		SAC [1]
2.8.	SAF	SAFE_T04	Analysis of On-treatment Percentage Change from Baseline in Bone Mineral Density (g/cm^2) at the Total Hip		SAC [1]
2.9.	SAF	SAFE_T04	Analysis of On-treatment Percentage Change from Baseline in Bone Mineral Density (g/cm^2) at the Total Hip by Gender		SAC [1]
2.10.	SAF	SAFE_T05	On-treatment Bone Mineral Density (g/cm^2) at the Total Hip Mixed Model Repeated Measures Analysis Interaction Test		SAC [1]

Safety:	Safety: Tables					
No.	Population	IDSL / Example Shell	Title	Programming Notes	Deliverable [Priority]	
BMD at	t Lumbar Spine	(L1-L4)				
2.11.	SAF	SAFE_T01	Summary of On-treatment Bone Mineral Density (g/cm^2) at the Lumbar Spine		SAC [1]	
2.12.	SAF	SAFE_T01	Summary of On-treatment Bone Mineral Density (g/cm^2) at the Lumbar Spine by Gender		SAC [1]	
2.13.	SAF	SAFE_T02	Summary of On-treatment Percentage Change in Bone Mineral Density (g/cm^2) at the Lumbar Spine		SAC [1]	
2.14.	SAF	SAFE_T02	Summary of On-treatment Percentage Change in Bone Mineral Density (g/cm^2) at the Lumbar Spine by Gender		SAC [1]	
2.15.	SAF	SAFE_T03	Summary of On-treatment T and Z Scores for Bone Mineral Density at the Lumbar Spine		SAC [1]	
2.16.	SAF	SAFE_T03	Summary of On-treatment T and Z Scores for Bone Mineral Density at the Lumbar Spine by Gender		SAC [1]	
2.17.	SAF	SAFE_T04	Analysis of On-treatment Percentage Change from Baseline in Bone Mineral Density (g/cm^2) at the Lumbar Spine		SAC [1]	
2.18.	SAF	SAFE_T04	Analysis of On-treatment Percentage Change from Baseline in Bone Mineral Density (g/cm^2) at the Lumbar Spine by Gender		SAC [1]	
2.19.	SAF	SAFE_T05	On-treatment Bone Mineral Density (g/cm^2) at the Lumbar Spine Mixed Model Repeated Measures Analysis Interaction Test	Only include the interaction for gender	SAC [1]	

Safety:	Tables				
No.	Population	IDSL / Example Shell	Title	Programming Notes	Deliverable [Priority]
Vital Si	gns, Incidence	of Fracture, Pneu	monia, X-rays and COPD Exacerbations		
2.20.	SAF	VS1	Summary of Vital Signs	All variables to have a row for minimum and maximum ontreatment values along with having a row for early withdrawal.	SAC [1]
2.21.	SAF	VS1	Summary of Change from Baseline in Vital Signs	All variables to have a row for minimum and maximum ontreatment values along with having a row for early withdrawal.	SAC [1]
2.22.	SAF	SAFE_T07	Summary of On-treatment Pneumonia		SAC [1]
2.23.	SAF	SAFE_T08	Summary of On-treatment Fractures		SAC [1]
2.24.	SAF	SAFE_T09	Summary of On-treatment Moderate/Severe COPD Exacerbations		SAC [1]
2.25.	SAF	SAFE_T09	Summary of On-treatment Severe COPD Exacerbations		SAC [1]
Spiron	netry				
2.26.	SAF	SAFE_T10	Summary of On-treatment FEV 1 (L) at Clinic Visits		SAC [1]
2.27.	SAF	SAFE_T10	Summary of On-treatment FVC (L) at Clinic Visits		SAC [1]
Advers	e Events			·	
2.28.	SAF		Overview of On-treatment Adverse Events During the Study		SAC [1]
2.29.	SAF	AE1	Summary of On-treatment Adverse Events Leading to Permanent Discontinuation of Study Treatment or Withdrawal from the Study by System Organ Class and Preferred Term	IDSL - Include rates.	SAC [1]

Safety:	Safety: Tables					
No.	Population	IDSL / Example Shell	Title	Programming Notes	Deliverable [Priority]	
2.30.	SAF	AE1	Summary of On-treatment Adverse Events by System Organ Class and Preferred Term	ICH E3. Include rates.	SAC [1]	
2.31.	SAF	AE1	Summary of On-treatment Adverse Events by Age	IDSL. Use age ranges: 40 to ≤ 65, >65 to ≤ 74, and ≥75	SAC [1]	
2.32.	SAF	AE1	Summary of On-treatment Adverse Events by Region	IDSL, North America vs Europe	SAC [1]	
2.33.	SAF	AE1	Summary of On-treatment Adverse Events by Gender	IDSL	SAC [1]	
2.34.	SAF	AE1	Summary of On-treatment Adverse Events by Smoking Status	IDSL	SAC [1]	
2.35.	SAF	AE1	Summary of Post-treatment Adverse Events by System Organ Class and Preferred Term	ICH E3. Include rates.	SAC [1]	
2.36.	SAF	AE1	Summary of On-treatment Drug-related Adverse Events by System Organ Class and Preferred Term	Include rates.	SAC [1]	
2.37.	SAF	AE1	Summary of On-treatment Drug Related Adverse Events	Number and % of subjects	SAC [1]	
2.38.	SAF	AE1	Summary of On-treatment Drug Related Serious Adverse Events	Number and % of subjects	SAC [1]	
2.39.	SAF	AE3	Summary of Common (>=3%) On-treatment Adverse Events by Overall Frequency	ICH E3	SAC [1]	
2.40.	SAF	AE15	Summary of Common (>=3%) Non-serious Adverse Events by System Organ Class and Preferred Term (Number of Subjects and Occurrences)	FDAAA, EudraCT	SAC [1]	
Seriou	s Adverse Even	nts				
2.41.	SAF	AE1	Summary of On-treatment Serious Adverse Events by System Organ Class and Preferred Term		SAC [1]	
2.42.	SAF	AE16	Summary of Serious Adverse Events by System Organ Class and Preferred Term (Number of Subjects and Occurrences)	FDAAA, EudraCT. Include rates.	SAC [1]	

Safety:	Tables						
No.	Population	IDSL / Example Shell	Title	Programming Notes	Deliverable [Priority]		
2.43.	SAF	AE1	Summary of On-treatment Serious Adverse Events Leading to Permanent Discontinuation of Study Treatment by System Organ Class and Preferred Term	IDSL	SAC [1]		
2.44.	SAF	AE16	Summary of On-treatment Fatal Serious Adverse Events by System Organ Class and Preferred Term		SAC [1]		
2.45.	SAF	AE16	Summary of On-treatment Non-fatal Serious Adverse Events by System Organ Class and Preferred Term		SAC [1]		
2.46.	SAF	AE16	Summary of On-treatment Drug-related Serious Adverse Events by System Organ Class and Preferred Term		SAC [1]		
Advers	Adverse Events of Special Interest						
2.47.	SAF	AE1	Summary of On-treatment Adverse Events of Special Interest	Include rates.	SAC [1]		
2.48.	SAF	AE1	Summary of On-treatment Serious Adverse Events of Special Interest	Include rates.	SAC [1]		

## 9.9.7. Safety Figures

Safety:	Figures				
No.	Population	IDSL / Example Shell	Title	Programming Notes	Deliverable [Priority]
BMD					
2.1.	SAF	SAFE_F01	Raw Geometric Percentage Change from Baseline in Ontreatment Bone Mineral Density (g/cm^2) at the Total Hip Over Time		SAC [1]
2.2.	SAF	SAFE_F01	Raw Geometric Percentage Change from Baseline in Ontreatment Bone Mineral Density (g/cm^2) at the Total Hip Over Time By Gender		SAC [1]
2.3.	SAF	SAFE_F01	Adjusted Mean Percentage Change from Baseline in Ontreatment Bone Mineral Density (g/cm^2) at the Total Hip	Add -1% per year clinical non-inferiority boundary with footnote.	SAC [1]
2.4.	SAF	SAFE_F01	Adjusted Percentage Change from Baseline in On-treatment Bone Mineral Density (g/cm^2) at the Total Hip Over Time		SAC [1]
2.5.	SAF	SAFE_F01	Adjusted Percentage Change from Baseline in On-treatment Bone Mineral Density (g/cm^2) at the Total Hip Over Time by Gender		SAC [1]
2.6.	SAF	SAFE_F01	Raw Geometric Percentage Change from Baseline in Ontreatment Bone Mineral Density (g/cm^2) at the Lumbar Spine Over Time		SAC [1]
2.7.	SAF	SAFE_F01	Raw Geometric Percentage Change from Baseline in Ontreatment Bone Mineral Density (g/cm^2) at the Lumbar Spine Over Time by Gender		SAC [1]
2.8.	SAF	SAFE_F01	Adjusted Percentage Change per Year from Baseline in Ontreatment Bone Mineral Density (g/cm^2) at the Lumbar Spine	Add -1% per year clinical non-inferiority boundary with footnote.	SAC [1]

2.9.	SAF	SAFE_F01	Adjusted Mean Percentage Change from Baseline in Ontreatment Bone Mineral Density (g/cm^2) at the Lumbar Spine Over Time		SAC [1]	
2.10.	SAF	SAFE_F01	Adjusted Mean Percentage Change from Baseline in Ontreatment Bone Mineral Density (g/cm^2) at the Lumbar Spine Over Time by Gender		SAC [1]	
Advers	Adverse Events					
2.11.	SAF	AE10	Plot of Common (>=3%) On-treatment Adverse Events and Relative Risk	IDSL	SAC [1]	

## 9.9.8. ICH Listings

ICH: Li	stings				
No.	Population	IDSL / Example Shell	Title	Programming Notes	Deliverable [Priority]
Subjec	t Disposition				
1.	Screened	ES7	Listing of Reasons for Screen and Run-in Failure	Journal Guidelines	SAC [1]
2.	SAF	ES2	Listing of Reasons for Study Withdrawal	ICH E3	SAC [1]
3.	SAF	BL1	Listing of Subjects for Whom the Treatment Blind was Broken	ICH E3	SAC [1]
4.	SAF	TA1	Listing of Planned and Actual Treatments	IDSL	SAC [1]
Protoc	ol Deviations			·	
5.	SAF	DV2	Listing of Important Protocol Deviations	ICH E3	SAC [1]
6.	SAF	IE3	Listing of Subjects with Inclusion/Exclusion Criteria Deviations	ICH E3	SAC [1]
Popula	tions Analysed				
7.	SAF	SP3	Listing of Subjects Excluded from the Safety Population	ICH E3. Note: Only create if this population is used.	SAC [1]
Demog	raphic and Bas	eline Characteris	tics		
8.	SAF	DM2 / DM4	Listing of Demographic Characteristics	ICH E3	SAC [1]
9.	SAF	DM9 / DM10	Listing of Race	ICH E3	SAC [1]
Exposi	ire and Treatmo	ent Compliance			
10.	SAF	EX3	Listing of Exposure Data	ICH E3	SAC [1]
Advers	e Events				
11.	SAF	AE8	Listing of All Adverse Events	ICH E3	SAC [1]
12.	SAF	AE7	Listing of Subject Numbers for Individual Adverse Events	ICH E3	SAC [1]
13.	SAF	AE2	Listing of Relationship Between Adverse Event System Organ Classes, Preferred Terms, and Verbatim Text	IDSL	SAC [1]

ICH: Lis	stings				
No.	Population	IDSL / Example Shell	Title	Programming Notes	Deliverable [Priority]
Serious	and Other Sig	nificant Adverse	Events		
14.	SAF	AE8	Listing of All Serious Adverse Events	ICH E3	SAC [1]
15.	SAF	AE8	Listing of Fatal Serious Adverse Events	ICH E3	SAC [1]
16.	SAF	AE8	Listing of Non-Fatal Serious Adverse Events	ICH E3	SAC [1]
17.	SAF	AE14	Listing of Reasons for Considering as a Serious Adverse Event	ICH E3	SAC [1]
18.	SAF	AE8	Listing of Non-Serious Adverse Events Leading to Withdrawal from Study / Permanent Discontinuation of Study Treatment	ICH E3	SAC [1]
19.	SAF	AE8	Listing of Serious Adverse Events Leading to Withdrawal from Study / Permanent Discontinuation of Study Treatment	ICH E3	SAC [1]
Hepato	biliary (Liver)				
20.	SAF	MH2	Listing of Medical Conditions for Subjects with Liver Stopping Events	IDSL	SAC [1]
21.	SAF	SU2	Listing of Substance Use for Subjects with Liver Stopping Events	IDSL	SAC [1]
All Lab	oratory				
22.	SAF	LB14	Listing of Laboratory Data	ICH E3	SAC [1]
Bone M	lineral Density				
23.	SAF	SAFE_L01	Listing of Bone Mineral Density, T and Z Scores at the Total Hip		SAC [1]
24.	SAF	SAFE_L01	Listing of Bone Mineral Density, T and Z Scores at the Lumbar Spine		SAC [1]

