Any subject who performs a Visit 1 procedure but does not continue in the study beyond Visit 1 or any subject who completes Visit 1 and enters the run-in period, but is subsequently found to be ineligible for the study (e.g. exclusionary laboratory, ECG, or spirometry findings) conducted prior to randomization to the study treatment medication (Visit 2), is classified as a 'screen failure'.

The study interactive voice response system (IVRS) will be contacted to report pre-screen failures. The following information will be collected for subjects who are pre-screen failures:

- Subject number
- Date of ICF signature
- Demographic information including race, age and gender
- Details of COPD medications within 30 days of Visit 0
- Details of COPD exacerbation (yes/no status), if applicable
- Serious Adverse Event information, if applicable, only for an SAE considered as related to study participation (e.g. study treatment, protocol mandated procedures, invasive tests, or change in existing therapy) or related to a GSK concomitant medication
- Investigator signature page

IVRS will be contacted to report screen failures. In addition to the information above, the following information will be collected for screen failures:

- Date of screening visit
- Reason for screen failure (screening failure and inclusion/exclusion criteria)

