6.2.6. COPD Exacerbations and Pneumonias

For the purpose of this study, exacerbation of COPD is defined by a worsening of symptoms requiring additional treatment as follows:

- A mild COPD exacerbation: managed by subject with increased use of prn medications
- A moderate COPD exacerbation: requires treatment with antibiotics and/or systemic corticosteroids
- A severe COPD exacerbation: requires hospitalization

Any subject experiencing worsening of symptoms should:

- Contact his/her study investigator and/or research coordinator immediately, and report to the study clinic as required
- If the subject is unable to contact his/her study investigator and/or research coordinator, they should contact their primary care physician (or other health care practitioner as required) and contact their study site as soon as possible
- If the subject seeks emergent/acute care for worsening respiratory symptoms, he/she should inform the caring Health Care Provider (HCP) to contact the investigator as soon as possible.

Subjects with presence of worsening respiratory symptoms will be classified by the Investigator as having:

• A mild/moderate/severe COPD exacerbation and/or pneumonia

OR

- A lower respiratory tract infection (LRTI) [i.e. other than pneumonia]
- Background variability of COPD
- A non-respiratory related disease
- Other respiratory related disease

The time period for collection of COPD exacerbations will begin from the time of Visit 2 (Randomization) and will end when the 7 ± 2 day Follow-up period has been completed.

COPD exacerbations should not be recorded as an adverse event, unless they meet the definition of a Serious Adverse Event. For the purposes of this study, COPD exacerbations will be collected and recorded on the exacerbation log in the eCRF. Exacerbations that meet the definition of an SAE, will be recorded on the appropriate eCRF section and should be reported to GSK for all subjects regardless of whether or not they are randomized to blinded study medication.

Subjects are excluded from participating if any of the following apply:

- They have poorly controlled COPD, defined as the occurrence of the following in the 12 weeks prior to Screening Visit 1: Acute worsening of COPD that is managed by the subject with corticosteroids or antibiotics or that requires treatment prescribed by a physician or requires hospitalization.

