8.3. Data Analysis Considerations

8.3.1. Analysis Populations

All Subjects Enrolled Population: This population will consist of all subjects, for whom a record exists on the study database, including screen failures and any subject who was not screened but signed the informed consent form. This population will be used for reporting subject disposition, reasons for withdrawal prior to randomisation, and inclusion, exclusion and randomisation criteria deviations and SAEs for non-randomised subjects.

(Modified) Intent-to-Treat (ITT) Population: This population will consist of all subjects who are randomised and receive at least one dose of study drug. The ITT Population will be the primary population for all analyses of safety and efficacy measures.

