8.3.5.2.2. Adverse Events (AEs)

AEs will be coded using the standard GSK dictionary, Medical Dictionary for Regulatory Activities (MedDRA), and grouped by body system. AEs occurring pre-treatment, during active treatment and post-treatment will be summarized separately. The number and percentage of subjects experiencing at least one AE of any type, AEs within each body system and AEs within each preferred term will be presented for each treatment group. Separate summaries will be provided for all AEs, drug related AEs, SAEs, and for AEs leading to withdrawal.

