### 4. ANALYSIS POPULATIONS

Population	Definition / Criteria	Analyses Evaluated
All subjects enrolled (ASE)	
 
All subjects for whom a record exists on the study database, including screen failures and any subjects who were not screened but signed the informed consent form.
 
	Study Population
Pre-screen, Screen and Run- in Failures (SRIF)	
 
All subjects who were enrolled but were either pre- screen failures, screen failures, run-in failures or subjects randomised in error.
 
	Study Population
Randomised	
 
All subjects who were given a randomisation number, including subjects who were randomised in error.
 
	Study Population
(Modified) Intent to treat (ITT)	
 
All randomised subjects who received at least one dose of study treatment.
 
This population will be based on the treatment the subject was randomised to.
 
	Study Population
Safety (SAF)	
 
All randomised subjects who received at least one dose of study treatment.
 
This population will be based on the treatment the subject took for the majority of the treatment period (>50%).
 
	

Study Population

Safety

Safety excluding closed sites	
 
This population would be the same as the safety population but excluding any sites that were closed due to audit findings, failures to adhere to GCP or any other findings.
 
This population will not be used unless there is a need to exclude sites.
 
	

Study Population

Safety

Refer to Appendix 12: List of Data Displays which details the population used for each display.

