46.	SAF	VS4	Listing of Myocardial infarction/unstable angina		SAC [1]		
47.	SAF	VS4	Listing of Congestive heart failure		SAC [1]		
48.	SAF	VS4	Listing of Arrhythmias		SAC [1]		
49.	SAF	VS4	Listing of Valvulopathy		SAC [1]		
50.	SAF	VS4	Listing of Pulmonary hypertension		SAC [1]		
51.	SAF	VS4	Listing of Cerebrovascular events/stroke and transient ischemic attack		SAC [1]		
52.	SAF	VS4	Listing of Peripheral arterial thromboembolism		SAC [1]		
53.	SAF	VS4	Listing of Deep venous thrombosis/pulmonary embolism		SAC [1]		
54.	SAF	VS4	Listing of Revascularisation		SAC [1]		
55.	SAF	VS4	Listing of Deaths		SAC [1]		

HZC102972

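### SAEs and deaths in subjects who are never dosed appear in no planned SAP table or listing, although the protocol commits to reporting SAEs in non-randomised subjects

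*SAP*

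**What the plan says.** **Protocol.** Section 8.3.1 lists what the ASE population is for, ending with "inclusion, exclusion and randomisation criteria deviations and SAEs for non-randomised subjects". Section 8.3.5.2.2 adds that "AEs occurring pre-treatment, during active treatment and post-treatment will be summarized separately". Section 8.3.5.2.3 promises case narratives for deaths and SAEs without naming a population.

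The protocol also collects such events before dosing. For pre-screen and screen failures, section 4.5 asks for "Serious Adverse Event information, if applicable, only for an SAE considered as related to study participation" or to one of the sponsor's concomitant medications. Section 6.2.13 records the same two kinds of SAE from consent. Section 6.2.6 says that exacerbations meeting the SAE definition "should be reported to GSK for all subjects regardless of whether or not they are randomized to blinded study medication".

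**SAP.** Section 4 defines ASE as "All subjects for whom a record exists on the study database, including screen failures and any subjects who were not screened" but who consented, and marks it for study-population analyses only. The Safety population (SAF) is randomised subjects with at least one dose. In section 9.9.8 the "Listing of All Serious Adverse Events" is on SAF, and in section 9.9.9 so is the "Listing of Deaths".

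**The concern.** The protocol names a population for SAEs outside the randomised set, and the SAP assigns no SAE display to it. A listing whose title claims completeness would omit every subject who never took double-blind drug.

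The pre-randomisation phase is not free of study-driven risk. Use of an ICS or LABA at Visit 2 is exclusionary (Protocol 4.3, criterion 21), and the run-in inhaler is placebo (5.5). Section 6.2.13 itself gives a change in existing therapy as one way an SAE can be related to participation. At stake is the completeness of the safety report for people who entered the study's procedures but were not treated.

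**Working it through.** No stated figure needs reproducing. The check compares the protocol's rule with the population column of the SAP's display list (9.9.4 to 9.9.9).

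**1. SAE and death displays.**

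| Displays | Count | Population |
|---|---|---|
| Tables 2.38, 2.41–2.46, 2.48 (SAEs) | 1 + 6 + 1 = 8 | SAF |
| Listings 14–17 and 19 (SAEs) | 4 + 1 = 5 | SAF |
| Listing 55 (deaths) | 1 | SAF |
| Total | 14 | 14 of 14 on SAF |

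The general AE displays that could also contain SAEs (Tables 2.28–2.40, Listings 11–13) are on SAF too.

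**2. Where the wider populations are used.** Enrolled, screen/run-in failure and screened populations appear only for study populations, enrolment by site, age ranges, failed criteria, and reasons for failure (Tables 1.1, 1.3, 1.4, 1.8, 1.11; Listing 1). None of these shows an SAE or a death.

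**3. Whether the change is declared.** SAP Table 1 covers the repeated-measures model, the addition of the Safety population, and the power table. It says nothing about SAEs in non-randomised subjects.

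**4. Who is left out.** SAF restricts subjects, not event dates. Listings 14–17 and Table 2.42 have no on-treatment limit in their titles, and SAP 9.4.3 defines a pre-treatment phase. So:
- An SAE before treatment in a subject later dosed can appear in Listing 14 and possibly in Table 2.42.
- An SAE in a subject never dosed cannot appear. SAP 9.4 assigns such events to the pre-treatment phase, but no SAE display includes the subject.
- A subject who dies in screening or run-in is never dosed, so that death cannot reach Listing 55.

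**5. An example from the protocol's own rules.** A hospitalisation for an exacerbation in run-in is a severe exacerbation (6.2.6). Exclusion criterion 8 bars a subject with a moderate or severe exacerbation in run-in. If the criteria are followed, that subject becomes a run-in failure and cannot enter SAF.

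**6. Scale.** Protocol 4.1 plans to screen about 400 to randomise about 280: 400 − 280 = 120, and 120/400 = 30%. Any randomised but undosed subjects add to this. The protocol's sentence does not strictly cover them, since they are randomised, but they are in ASE and outside SAF in the same way.

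**7. The separate capture question.** Section 6.2.6 requires serious exacerbations to be reported whatever the randomisation status. Sections 4.5 and 6.2.13 limit pre-treatment SAEs to those related to participation or to a sponsor concomitant medication; Table 3 footnote 12 mentions only the first. For a serious run-in exacerbation judged unrelated, these rules give different answers.

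**The case against.** The strongest reply is that a missing display is not a missing report. Narratives under Protocol 8.3.5.2.3 have no population limit, so a death in run-in could still be narrated. SAP 6.1.1 counts subjects with run-in exacerbations, though not by seriousness. AE outputs follow sponsor standards, and the display specifications are available only on request, so neither can be checked here. Expedited SAE reporting to the sponsor does not depend on these listings. All of this stands, and it limits the claim to planned tables and listings.

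Three stronger readings are tempting but unsupported:
- *That all run-in SAEs drop out of the report.* They do not: those in subjects later dosed can still be listed, and narratives remain possible.
- *That 120 subjects each contribute up to 21 days of unreported run-in.* Section 4.5 counts as screen failures people who stop at Visit 1, who have no run-in, and the documents give no split.
- *That the absent pre-treatment AE table is a large loss.* AEs are collected only from the start of double-blind drug (6.2.8), so that table would hold little beyond the few SAEs already discussed.

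It is also fair that few events are likely, because capture before Visit 2 is narrow. None of this supplies a display that meets the commitment in Protocol 8.3.1.

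**Conclusion.** The point holds for subjects never dosed. The protocol says ASE will be used to report SAEs in non-randomised subjects; the SAP puts 14 of 14 SAE and death displays on SAF and does not declare the change. About 120 of 400 screened subjects (30%) have no SAE or death display, assuming the approximate numbers in Protocol 4.1 are met. The number of affected events cannot be derived from the documents and is probably small.

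This is a defect in the completeness of safety reporting and should be corrected. It does not affect the BMD analysis, the treatment comparison or on-treatment safety. The capture-rule mismatch is a separate protocol inconsistency.

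**What to change.** **SAP.** Either of these would do:
- run Listings 14–17 and 55 on ASE, with columns for randomised/dosed status and study phase; or
- keep them on SAF and add one ASE listing of SAEs and deaths in never-dosed subjects.

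In both cases add one line counting never-dosed subjects with an SAE and with a death. State in a footnote which pre-randomisation SAEs were collected: unrelated, non-exacerbation SAEs before Visit 2 are not recorded, so even an ASE listing would not hold every SAE. If the sponsor instead means to depart from Protocol 8.3.1, SAP Table 1 should say so and why; that would make the choice visible but would not supply the missing display.

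The cost is a population entry and columns on five listings, or one new listing, plus the count line. No new data are needed for events already captured.

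**Protocol, separately.** Sections 6.2.6, 4.5, 6.2.13 and Table 3 footnote 12 must be reconciled on which pre-randomisation SAEs are captured. This changes protocol text and is not part of the cost of the listing fix.
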